4. STUDY POPULATION

4.1 Inclusion criteria

Patients meeting the following criteria may enter the study:

1. Patients must have given written informed consent.
2. Female or male aged 18 years and over.
3. Diagnosis of metastatic malignancy to the liver and no detectable malignant disease outside the liver or diagnosis of metastatic malignancy to the liver with limited disease outside the liver (i.e. liver-dominant disease) defined as the sum of the diameters of all metastases in the liver to be more than 200% of the sum of the diameters of all soft tissue lesions outside the liver.
4. Patient is not amenable for standard therapies (other than radioembolization) or patient refuses standard therapies for reasons of toxicity
5. Life expectancy of 12 weeks or longer.
6. World Health Organisation (WHO) Performance status 0-2 (see Appendix III).
7. One or more measurable lesions at least 10 mm in the longest diameter by spiral CT according to the Response Evaluation Criteria in Solid Tumours (RECIST) 1.1 criteria.
8. Negative pregnancy test for women of childbearing potential.

4.2 Exclusion criteria

Patients meeting any of the following criteria cannot enter the study:

1. Brain metastases or spinal cord compression, unless irradiated at least 4 weeks prior to the date of the experimental treatment and stable without steroid treatment for at least 1 week.
2. Radiation therapy within the last 4 weeks before the start of study therapy.
3. The last dose of prior chemotherapy has been received less than 4 weeks prior the start of study therapy.
4. Major surgery within 4 weeks, or incompletely healed surgical incision before starting study therapy.
5. Any unresolved toxicity greater than National Cancer Institute (NCI), Common Terminology Criteria for Adverse Events (CTCAE version 4.0, see Appendix II) grade 2 from previous anti-cancer therapy.
6. Serum bilirubin > 1.5 x Upper Limit of Normal (ULN).
7. Glomerular filtration rate <35 ml/min, determined according to the Modification of Diet in Renal Disease formula.
8. Alanine aminotransferase (ALT), aspartate aminotransferase (AST), or alkaline phosphatase (ALP) > 5 x ULN.
9. Leukocytes < 4.0 10⁹/l and/or platelet count < 150 10⁹/l.
10. Significant cardiac event (e.g. myocardial infarction, superior vena cava (SVC) syndrome, New York Heart Association (NYHA) classification of heart disease ≥2 within 3 months before entry, or presence of cardiac disease that in the opinion of the Investigator increases the risk of ventricular arrhythmia.
11. Pregnancy or breast feeding (women of child-bearing potential).
12. Patients suffering from diseases with a increased chance of liver toxicity, such as primary biliary cirrhosis or xeroderma pigmentosum.
13. Patients suffering from psychic disorders that make a comprehensive judgement impossible, such as psychosis, hallucinations and/or depression.
14. Patients who are declared incompetent.
15. Previous enrolment in the present study or previous treatment with radioembolization.

16. Treated with an investigational agent within 42 days prior to starting study treatment.
17. Female patients who are not using an acceptable method of contraception (oral contraceptives, barrier methods, approved contraceptive implant, long-term injectable contraception, intrauterine device or tubal ligation) OR are less than 1 year postmenopausal or surgically sterile during their participation in this study (from the time they sign the consent form) to prevent pregnancy.
18. Male patients who are not surgically sterile or do not use an acceptable method of contraception during their participation in this study (from the time they sign the consent form) to prevent pregnancy in a partner.
19. Patients with abnormalities of the bile ducts (such as stents) with an increased chance of infections of the bile ducts. Or evidence of extensive portal hypertension, splenomegaly, ascites or active hepatitis (B and/or C).
20. Body weight over 150 kg.
21. Moderate or severe adverse reaction to i.v. contrast (Visipaque[®]), as defined by the ACR Manual on Contrast Media - Version 9 (2013) (see Appendix XIV).
22. MRI contra-indications: severe claustrophobia, metal shrapnel, implanted pacemaker and/or neurostimulators.
23. Liver tumour involvement $\geq 70\%$ as quantified on CT

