5.2.2 Pretreatment visit

Patients will be hospitalized on the evening before the day of the pretreatment angiography. They will be discharged approximately 24 hours after the intervention unless complications occur. The screening visit can coincide with the pretreatment and treatment visit, if so, duplicate procedures need not be performed. If the treatment is shortly after the pretreatment, the hospital stay can be extended for the duration of that visit. During this visit, the following must be documented and reviewed as a part of the study:

- Inclusion and exclusion criteria
- Physical examination (incl. vital signs)
- Pregnancy test for women of childbearing age
- WHO performance assessment
- Concomitant medication
- Monitoring of occurrence of (serious) adverse events
- Laboratory examination type A (blood)
- Pretreatment angiography, administration of ^{99m}Tc -MAA
- ^{99m}Tc -MAA SPECT/CT

On day 0, the patient is subjected to an angiography of the upper abdominal vessels. At least the celiac axis and superior mesenteric artery are visualised, followed by coiling of relevant vessels, especially branches of the celiac axis supplying non-target organs. This procedure will be performed by a skilled and trained interventional radiologist. The catheter is introduced using the Seldinger technique. Prior to the procedure the patient is offered a tranquilizer. Premedication consists of proton pump inhibitors (pantoprazol 1 dd 40 mg), starting at the day of the intervention. Proton pump inhibitors are prescribed to the patients to be used until 3 months post ^{166}Ho -RE.

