5.2.3 Treatment visit

The second intervention takes place around 1 week after the first intervention but not later than 3 weeks after. Patients will be hospitalized on the evening before the day of treatment. They will be discharged approximately 24 hours after the intervention unless complications occur. During this visit, the following must be documented and reviewed as a part of the study:

- Inclusion and exclusion criteria
- Physical examination (incl. vital signs)
- WHO performance assessment
- Concomitant medication
- Pretreatment MRI
- Treatment angiography, administration of scout dose of ^{166}Ho -PLLA-MS
- Post scout dose SPECT/CT

- Post scout dose MRI or post scout- and post therapy dose ^{166}Ho -PET/CT
- Treatment angiography, administration of therapy dose of ^{166}Ho -PLLA-MS
- Post treatment MRI
- Monitoring of occurrence of (serious) adverse events
- Collecting of 24-hours urine for holmium content (using either a condom-catheter or an Foley catheter)
- Laboratory examination type A and C (blood and urine)
- Radiation exposure rate

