5.6 Use of co-medication / prophylactic measures

All patients that are eligible for the experimental treatment will receive proton pump inhibitors (pantoprazol 1 dd 40 mg) starting the day before the catheterisation, which will be continued for 6 weeks.

All patients that are eligible for the experimental treatment will receive anti-emetic drugs (ondansetron i.v. 8mg) and prevention of contrast allergy (dexamethason 16mg p.o. and 10mg i.v. and clemastine 1mg p.o.) prior to catheterisation.

During the vascular intervention the patient will receive heparin (1000 IU/ml in saline, up to 5000 IU), to avoid the formation of thromboembolism during the intervention.

The vascular intervention will be performed under x-ray guidance. To be able to visualise the blood vessels during the procedure, a non-ionogenic x-ray contrast agent (jodixanol, Visipaque[®]) will be administered to the patient.

Should women of childbearing age require microsphere therapy, non-pregnancy needs to be ascertained prior to treatment. Therefore, proper contraceptive measures should be used, such as the birth control pill.

As a prophylactic measure for thromboembolic events, all patients will be provided with pressure stockings at the day of each angiography. Patients will be advised to wear these pressure stockings until the end of hospitalization or until the moment that patient is able to mobilise.

After the angiography, when the urinary catheter is removed, patients receive a single gift of amoxicillin/clavulanic acid (1000/200mg i.v.) for prevention of urinary tract infections.

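### Exclusions 17 and 18 are mis-worded: taken literally, 18 bars every man who is not surgically sterile, and 17 bars postmenopausal women using no contraception and, on its plain reading, surgically sterile women

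*Protocol*

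**What the plan says.** The exclusion list in section 4.2 opens with the rule "Patients meeting any of the following criteria cannot enter the study", so each criterion acts alone.

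- **Exclusion 18 (men):** "Male patients who are not surgically sterile or do not use an acceptable method of contraception during their participation in this study". The stated purpose is to prevent pregnancy in a partner.
- **Exclusion 17 (women), first limb:** "Female patients who are not using an acceptable method of contraception". The list of acceptable methods ends with "long-term injectable contraception, intrauterine device or tubal ligation".
- **Exclusion 17, second limb:** "OR are less than 1 year postmenopausal or surgically sterile during their participation in this study". The stated purpose is again to prevent pregnancy.
- **Related criteria:** inclusion 8 requires a negative pregnancy test for women of childbearing potential and gives no time window. Exclusion 11 uses the same term.
- **Test schedule:** Table 2 has one mark for the urine pregnancy test, in the pre-treatment column. Section 5.2.2 agrees: "Pregnancy test for women of childbearing age". The list for the treatment visit in section 5.2.3 includes a re-check of the inclusion and exclusion criteria but no pregnancy test.
- **Interval:** "The second intervention takes place around 1 week after the first intervention but not later than 3 weeks after" (section 5.2.3). If the scout dose looks suspect, a second technetium procedure follows after a week, then a new scout dose and the therapy dose.
- **General safeguard:** section 5.6 says "non-pregnancy needs to be ascertained prior to treatment", with no test, date or window.

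**The concern.** These are operative entry rules. Section 12.2 requires source documents to show that each patient satisfied all the criteria, and section 12.8 says the data will support a CE-marking application. Against the literal text, a fertile man using contraception, or a postmenopausal woman using none, is an eligibility deviation if enrolled. The alternative is that staff apply a rule other than the written one, each in their own way.

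The pregnancy test raises a smaller question of the same kind. Eligibility is checked again at the treatment visit, but the protocol does not say whether that check rests on a fresh result or on the one from the pretreatment visit.

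**Working it through.** The plan gives no figure on this point to reproduce. The check is a truth table for each criterion and a count of days.

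**Exclusion 18.** Literal rule: exclude if (not sterile) or (no contraception). Evident intent: exclude if (not sterile) and (no contraception).

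| Surgically sterile | Uses contraception | Literal | Intended |
|---|---|---|---|
| no | no | excluded | excluded |
| no | yes | **excluded** | admitted |
| yes | no | **excluded** | admitted |
| yes | yes | admitted | admitted |

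The literal rule admits one of four combinations. The intended rule excludes one of four. They disagree on the two middle rows.

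**Exclusion 17.** Reading A is the plain one: exclude if no listed method, or less than 1 year postmenopausal, or surgically sterile. Reading B lets the one-year limit govern sterilisation as well. The intended rule exempts women who cannot conceive; it is modelled here as at least 1 year postmenopausal or surgically sterile.

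| Woman | A | B | Intended |
|---|---|---|---|
| Premenopausal, uses a method | admitted | admitted | admitted |
| Premenopausal, no method | excluded | excluded | excluded |
| Tubal ligation 1 year or more ago | **excluded** | admitted | admitted |
| Tubal ligation under 1 year ago | **excluded** | **excluded** | admitted |
| Hysterectomy 1 year or more ago, no listed method | **excluded** | **excluded** | admitted |
| Postmenopausal 1 year or more, no method | **excluded** | **excluded** | admitted |
| Postmenopausal under 1 year, uses a method | **excluded** | **excluded** | admitted |

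Reading A accepts tubal ligation in one limb and bars it in the other. Reading B removes that conflict only for ligations at least a year old. Under both readings the first limb still bars the postmenopausal woman and the woman after hysterectomy who use no listed method.

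**Age of the pregnancy test at the holmium doses.** Inputs: an interval of about 7 days, at most 21 (section 5.2.3), and admission on the evening before the pretreatment angiography (section 5.2.2).

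- Ordinary path: usually about 7 days, at most 21, or 21 + 1 = 22 if the test is done on the admission evening.
- Repeat path, if the test is not repeated: first interval + 7 + second interval. The protocol does not fix the second interval; I assume 0 to 21 days.
  - First interval 7: 7 + 7 + 0 = 14 to 7 + 7 + 21 = 35 days.
  - First interval 21: 21 + 7 + 0 = 28 to 21 + 7 + 21 = 49 days.
- Repeat path, if the test is repeated with the second technetium procedure: only the second interval counts, 0 to 21 days on the same assumption.

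**The case against.** The best defence is that everyone knows what is meant. Both criteria state their purpose, and read with it the rule is sterile or contracepting. That stands as to intent and keeps this a drafting error. It does not rescue the text: exclusion 18 repeats the negative after *or*, so it cannot be parsed as neither sterile nor contracepting. For exclusion 17, reading B is available and makes an older tubal ligation eligible, so the bar on sterile women is the plain reading and not the only one.

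A reader might infer several stronger things that the documents do not support:

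- *The criteria reject most of the intended population.* The protocol gives no sex, age or sterility figures, so the share affected is unknown.
- *The repeat path generally leaves a test 35 to 49 days old.* That takes the first interval at its 21-day maximum, a second interval of 7 to 21 days, and no retest. The visit that contains the technetium procedure lists the pregnancy test, and the protocol does not say whether that list applies again.
- *Section 5.6 is contradicted.* A test at the pretreatment visit is prior to treatment, and section 5.6 sets no window. Exclusion 11 is also re-checked at the treatment visit, and exclusion 17 concerns contraception from consent onwards. Section 5.2.2 further allows the hospital stay to be extended when treatment follows shortly, so the gap can be shorter than a week.
- *The test must precede the screening CT.* Section 5.2.1 calls the screening PET/CT part of the routine work-up, and no passage requires a test before it.

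**Conclusion.** Exclusions 17 and 18 are wrong as written and should be corrected. Exclusion 18 excludes every man who is not surgically sterile, whatever contraception he uses; this needs no assumption beyond the any-criterion rule. Exclusion 17 bars women long past menopause who use no listed method on either reading, and surgically sterile women in general on the plain reading. The primary endpoint, type I error and power are not affected.

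The test timing is a secondary gap and not a contradiction. The one scheduled result is at most 21 to 22 days old on the ordinary path. It is older on the repeat path only if the test is not repeated and the intervals add up to more. The documents settle neither, nor which result the re-check at the treatment visit uses.

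**What to change.** 1. **Exclusion 18:** replace *or* with *and*, so that it covers men who are neither surgically sterile nor using an acceptable method.
2. **Exclusion 17:** restate it as female patients of childbearing potential who do not use an acceptable method of contraception. Inclusion 8 and exclusion 11 already use that term. The sponsor should define it once and use it throughout, since sections 5.2.2 and 5.6 speak of childbearing age instead.
3. **Pregnancy test:** reconcile Table 2, sections 5.2.2, 5.2.3 and 5.6, and inclusion 8, so that they state which test result the treatment-visit re-check relies on, including after a second technetium procedure. What that rule should be is for the sponsor and investigators to decide.

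Items 1 and 2 change two sentences and add one definition; they add no visit, procedure or patient. Item 3 needs a clarifying sentence. Any cost beyond that depends on the rule chosen.

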5. TREATMENT OF PATIENTS

5.1 Schedule of procedures

Table 2: Schedule of study procedures

Procedures	Screening										
		pre-treatment	treatment	1w	3w	6w	9w	3m	6m	9m	12m
Informed consent	X										
In-/exclusion	X	X	X								
Demographic data	X										
Medical history	X										
Physical exam and WHO performance status	X	X	X		X	X	X	X	X	X	X
Pregnancy test (urine)		X									
EORTC Questionnaire	X			X		X		X	X	X	X
¹⁸ F FDG-PET/CT ¹	X							X	X	X	X
¹⁶⁶ Ho-PET/CT ²			XX								
MRI (diagnosis, response and holmium quantification) ³			XXX					X	X	X	X
Angiography		X	X								
Tc-99m-MAA administration		X									
Scout dose of ¹⁶⁶ Ho-PLLA-MS			X								
Therapy dose of ¹⁶⁶ Ho-PLLA-MS			X								
Scintigraphy (planar and SPECT/CT)		X ⁴	X ⁵	X ⁶							
Radiation exposure rate			X								
ECG	X										
Laboratory examination type A ⁷	X	X	X					X	X	X	X
Laboratory examination type B ⁷					X	X	X				
Laboratory examination type C ⁷			X								
Monitoring of (S)AE's + concomitant med.		X	X		X	X	X	X	X	X	X

¹. Positron Emission Tomography (PET) will only be performed in FDG-avid tumors.

². ¹⁶⁶Ho-PET/CT for biodistribution assessment will be performed one hour post scout dose and one hour post treatment dose. These PET-scans will only be performed in the 1st - 6th patient that receives treatment. After the 12th patient, patients will either receive ¹⁶⁶Ho-PET or ¹⁶⁶Ho-MR imaging

³. MRI for tumor response assessment and quantification one day prior to scoutdose. After scout dose, a non-contrast enhanced MRI of a limited duration (<15min) for quantification. After therapy all MRI's will be for tumor response assessment and quantification. The scout dose MRI will only be performed in the 7th - 12th patient that receives treatment. After the 12th patient, patients will either receive ¹⁶⁶Ho-PET or ¹⁶⁶Ho-MR imaging

⁴. Tc-99m-MAA scintigraphy

⁵. Scout dose scintigraphy

⁶. Post treatment scintigraphy

⁷. Laboratory examination type A (blood), B (blood) and C (blood and urine) see Table 3: Laboratory examinations

Table 3: Laboratory examinations

Laboratory examination	Parameters	
Type A (blood)	Hematology	Leukocytes, erythrocytes, hemoglobin (Hb), hematocrit (HCT), mean corpuscular volume (MCV), mean corpuscular hemoglobin (MCH), mean corpuscular hemoglobin concentration (MCHC), differential leukocyte count (neutrophils, lymphocytes, monocytes, eosinophils, basophils) and platelet count.
	Coagulation profile	Reagent-independent prothrombin ratio prothrombin time/ partial thromboplastin time (PT/PTT). If PT and/or PTT are out of range, Thrombin time (TT) will be automatically measured. Activated partial thromboplastin time (APTT).
	Serum chemistry	Creatinine, total bilirubin, alkaline phosphatase, SGPT/ALT, SGOT/AST, γ GT, glucose, chloride, calcium, potassium, sodium, total protein, albumin, bicarbonate, urea, magnesium, phosphorus, ammonia, LDH, CRP and relevant tumour markers.
Total: 10 ml		
Type B (blood)	Hematology	Leukocytes, erythrocytes, hemoglobin (Hb), hematocrit (HCT), mean corpuscular volume (MCV), mean corpuscular hemoglobin (MCH), mean corpuscular hemoglobin concentration (MCHC), differential leukocyte count (neutrophils, lymphocytes, monocytes, eosinophils, basophils) and platelet count.
	Serum chemistry	Creatinine, total bilirubin, alkaline phosphatase, SGPT/ALT, SGOT/AST, γ GT, glucose, albumin, ammonia, lactate dehydrogenase (LDH) and C-reactive protein (CRP).
	Total: 4 ml	
Type C (blood and urine)	Holmium content	Holmium content.
	Total blood: 7 ml	

5.2 Study procedures

5.2.1 Screening

The screening visit will take place within 14 days prior to the fist angiography. During this visit the following procedures must be documented and reviewed as a part of the screening process:

- Informed consent
- Inclusion and exclusion criteria
- Demographic data
- Medical and surgical history
- Previous and ongoing medications (within the last 3 months)
- Physical examination including height and weight
- Vital signs, including blood pressure (after at least 3 minutes sitting), pulse and temperature
- WHO performance assessment
- PET/CT (should be performed within 2 weeks prior to the first angiography). (PET/CT is part of the routine work-up for radioembolization. The PET part of the PET/CT examination will only be performed in FDG-avid tumours. The CT part of the PET/CT examination consists of a low dose CT and a diagnostic 3-phase CT of the liver. In non FDG-avid tumours, only a diagnostic 3-phase CT of the liver will be performed.
- Electrocardiogram (ECG)
- Laboratory examination type A (blood)
- European Organization for Research and Treatment of Cancer (EORTC) Quality of Life (QoL) questionnaire

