Prior to the procedure, the patient is offered a tranquilizer and a Foley catheter is inserted or a condom-catheter is applied for 24-hours urine collection. If a Foley catheter is used, the patient will receive a single dose of antibiotics 3 hours post ^{166}Ho -RE (therapy dose). An experienced interventional radiologist will administer the scout dose of ^{166}Ho -PLLA-MS through a catheter inside the hepatic artery at the position as planned during the first intervention. At the end of this angiography, the vascular sheath will remain in situ (femoral artery). This sheath will be used for the treatment angiography later that day. The vascular access site will be covered with a sterile patch. In addition, NaCl 0.9% under pressure will be connected to the sheath to prevent from clot formation. The patient will remain in supine position in his/her bed and will be transferred to the MRI / PET and SPECT scanners. In order to detect inadvertent administration to the lungs or other non-target organs (e.g. stomach, duodenum, pancreas) scintigraphy will be performed after administration of the scout dose of ^{166}Ho -PLLA-MS to assess its distribution. Both planar imaging of the thorax and abdomen will be performed, as well as SPECT of the abdomen. If the ^{166}Ho -PLLA-MS scout dose SPECT is suspect for extrahepatic deposition, after a week a second $^{99\text{m}}\text{Tc}$ -MAA procedure will be started. In this procedure the blood vessels that probably cause the extrahepatic deposition will be identified if possible. Based on the findings, the interventional radiologist might adapt the catheter position and/or coil the culprit extrahepatic vessels. In case the second $^{99\text{m}}\text{Tc}$ -MAA SPECT does not show extrahepatic deposition, a new ^{166}Ho -PLLA-MS scout dose will be administered. In case this second ^{166}Ho -PLLA-MS scout dose SPECT does not show extrahepatic deposition the ^{166}Ho -PLLA-MS therapy dose will be given. If again extrahepatic ^{166}Ho -PLLA-MS scout dose deposition occurs, the treatment will be terminated.

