8. METHODS

8.1 Study endpoints

8.1.1 Primary study endpoint

- The primary outcome is target lesions tumour response at three months follow-up. For this study, this is defined as: 1) complete response on CT at 3 months, or 2) partial response on CT at 3 months or 3) stable disease on CT at 3 months (see chapter 8.3.1 Definition of treatment success). Tumour size will be assessed on the portovenous phase of the dynamic contrast-enhanced CT images. At fixed intervals in time (3, 6, 9, and 12 months post ¹⁶⁶Ho-RE), the largest liver lesions are selected, to a maximum of two, and the maximum diameter in axial plane is measured. The sum of the maximum diameter of the lesions is recorded.
 - Complete Response (CR): disappearance of all lesions
 - Partial Response (PR): $\geq 30\%$ decrease in the sum of the longest diameters of target lesions, with the baseline measurements taken as reference
 - Stable Disease (SD): $<30\%$ decrease and $<20\%$ increase
 - Progressive Disease (PD): $\geq 20\%$ increase in the sum of the longest diameters of target lesions, with the baseline measurements taken as reference or appearance of new lesions

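### The response-baseline CT is timed to the first angiography, not to the therapy dose, so up to 5 weeks of pre-treatment growth (more after a repeat scout dose) can count against the primary endpoint.

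*Protocol*

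**What the plan says.** - **Baseline scan.** Section 5.2.1: "PET/CT (should be performed within 2 weeks prior to the first angiography".
- **Therapy dose.** Section 5.2.3: "The second intervention takes place around 1 week after the first intervention but not later than 3 weeks after".
- **Repeat route.** If the scout scan is "suspect for extrahepatic deposition, after a week a second" MAA procedure is started, followed, if clear, by a new scout dose and then therapy (section 5.2.3). No limit is given from the second MAA procedure to the therapy dose, and no new CT is listed.
- **Shorter gaps are possible.** Section 5.2.2: "The screening visit can coincide with the pretreatment and treatment visit, if so, duplicate procedures need not be performed".
- **Follow-up scan.** Section 5.2.8 sets it at 3 months after treatment, plus or minus 7 days.
- **Endpoint.** Section 8.1.1 reads the primary outcome on CT, "with the baseline measurements taken as reference". Progression is an increase of at least 20% in the summed diameters, or new lesions. Complete response, partial response and stable disease are all successes (section 8.3.1).
- **MRI.** Table 2, footnote 3: "MRI for tumor response assessment and quantification one day prior to scoutdose". MRI is repeated at 3 months but does not enter the primary endpoint.
- **Chemotherapy.** Exclusion 3 in section 4.2: "The last dose of prior chemotherapy has been received less than 4 weeks prior the start of study therapy". The protocol does not say whether study therapy starts at the first angiography or at the holmium dose.

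**The concern.** The primary endpoint is a change between two CT scans. The later scan is tied to the therapy dose within a week either way. The earlier one is tied to a different procedure, and nothing caps the time from it to the dose. What happens to the tumour in between is attributed to the treatment.

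Success means anything short of progression. Untreated growth in the gap spends part of the 20% allowance, and a lesion that appears before the dose is already progression. The amount spent depends on tumour growth rate and on how long the work-up took, so it differs between patients. It is largest in fast-growing disease and in patients who need a repeat work-up. At stake are the estimated success rate, which the Summary and section 10 name as an output, and the power of the sequential test.

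**Working it through.** **1. The plan's own figures.** The protocol states no CT-to-therapy interval, so there is none to reproduce. Its design figures do reproduce. An exact binomial recursion over Table 1 in section 3 (looks at 30, 36, 42 and 48 patients; lower boundaries 5, 6, 7, 15; upper 11, 13, 14, 16) gives a one-sided type I error of 0.0452 at 20% and power of 0.898 at 40%. The protocol states 4.5% and 90%. This point does not affect those figures; it affects the success rate that is put into them.

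**2. The gap, from the protocol's windows.** The repeat rows add 7 days to the second MAA procedure.

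| Route | Usual spacing | Every window at its limit |
|---|---|---|
| Single pass | 14 + 7 = 21 days | 14 + 21 = 35 days |
| Repeat scout | 14 + 7 + 7 + 7 = 35 days | 14 + 21 + 7 + 21 = 63 days |

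The last 7 or 21 days in the repeat row assume that the spacing of section 5.2.3 applies a second time. The protocol does not say so. All four are upper values, because the CT may be closer to the angiography than 14 days.

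**3. Growth in the gap.** Assume exponential growth with volume doubling time VDT. The diameter factor is 2^(gap / (3 × VDT)), and the margin left after the dose is 1.20 / factor − 1. The doubling times are assumptions, not protocol figures.

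| Gap | VDT 60 days | VDT 90 days | VDT 150 days |
|---|---|---|---|
| 21 days: growth / margin left | 8.4% / 10.7% | 5.5% / 13.7% | 3.3% / 16.2% |
| 28 days | 11.4% / 7.7% | 7.5% / 11.7% | 4.4% / 14.9% |
| 35 days | 14.4% / 4.9% | 9.4% / 9.7% | 5.5% / 13.7% |
| 63 days | 27.5% / none | 17.6% / 2.1% | 10.2% / 8.9% |

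Example: 2^(35/180) = 1.144 and 1.20/1.144 = 1.049. At a 63-day gap and a 60-day doubling time, a tumour fully arrested on the day of therapy is already classed as progressive.

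**4. What a lower rate costs.** As an illustration only, suppose the gap lowers a true 40% success rate to 35%. The same recursion then gives power of 0.720 instead of 0.898. The documents do not allow the actual shift to be estimated.

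**5. The chemotherapy path.** If the 28-day washout is counted to the holmium dose, chemotherapy could fall after the baseline CT for at most gap − 28 days:

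- 21- or 28-day gap: 0 days
- 35-day gap: 7 days
- 63-day gap: 35 days

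If it is counted to the first angiography, the opening is 0 days on every route.

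**The case against.** **Direction.** A reader might infer that untreated growth is credited to holmium. The endpoint rules say the opposite: growth before the dose raises the 3-month sum relative to baseline and pushes patients towards failure. In a single-arm test against 20% this cannot raise the type I error. That objection stands.

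**Size of the gap.** A reader might also take 5 to 9 weeks as the normal gap. The protocol plans the second intervention about a week after the first, so 21 days is the usual ceiling and 35 days the single-pass limit. Nine weeks needs a suspect scout scan, every window at its limit, and a spacing rule that is not stated for the second pass. The protocol gives no frequency for the repeat route.

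**Chemotherapy.** This is the only path examined here that could favour the device, and it is nearly closed. Inclusion 4 (section 4.1) limits entry to patients not amenable to, or refusing, standard therapies, and eligibility is rechecked at the pretreatment and treatment visits. For scale only: a lift from 20% to 25% would raise the chance of a positive decision from 4.5% to 18.9%, but nothing in the documents suggests a lift of that size.

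**Benefit of a cap.** Under the assumed doubling times, moving from 35 to 28 days removes only about 1 to 3 points of diameter growth. That is correct; the larger gain is on the repeat route.

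**MRI.** Using CT for the primary endpoint is a consistent choice, and a sensitivity analysis or a gap listing is commonly left to an analysis plan. Their absence is not a fault.

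What remains is the missing link between baseline CT and therapy dose, which the protocol itself fixes.

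**Conclusion.** The point holds in a limited form. The baseline CT has no maximum distance from the therapy dose. The protocol's windows allow up to 35 days on a single pass, and the repeat-scout route has no stated limit and no new CT. The effect is mainly conservative: a lower and unevenly distorted success rate, and some loss of power. Growth of about 6% to 14% in 35 days and 10% to 27% in 63 days rests on assumed doubling times of 150 down to 60 days; the 63 days also rests on the 3-week limit applying twice. At the usual single-pass spacing of up to 21 days the effect is smaller, about 3% to 8%.

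The documents do not support a claim that the gap inflates apparent efficacy. A chemotherapy effect credited to holmium is a minor possibility, open only if the washout is counted to the holmium dose. The quoted sections do not contradict one another. This is a design gap that is cheap to close.

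**What to change.** 1. In section 5.2.1, set a maximum total interval from the response-baseline CT to the therapy dose. As an example, 28 days is already met at usual spacing (14 + 7 = 21). It is also met at the 3-week limit if the CT is taken within 7 days before the first angiography (7 + 21 = 28).
2. Require this CT to follow the last dose of any prior anticancer therapy, and state which event counts as the start of study therapy in section 4.2.
3. For patients who exceed the limit through the repeat-scout route, keep the CT-based primary analysis and add a sensitivity analysis of the pre-scout MRI against the 3-month MRI. Both are already scheduled. State which MRI is used: the protocol does not say whether it is repeated before a second scout dose. If it is not, under the spacing assumed above it precedes therapy by 1 + 7 + 7 = 15 to 1 + 7 + 21 = 29 days, still well short of 63.
4. Report the distribution of the CT-to-therapy gap.

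**Cost.** Protocol wording, slightly tighter scheduling of the screening CT and one extra analysis. No scan is added for single-pass patients.
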